# 7. Data Safety and Monitoring Plan

Data Safety and Monitoring Plan is set for ensuring the safety of patients. The plan is composed of three phases.

- (1) Screening and recruitment period
  - a. Screening patient by pre-set inclusion and exclusion criteria
  - b. Explain the current medical situation to patients, and alternative treatment methods
  - c. Obtain signed inform consent
- (2) Trial execution period
  - a. Conduction of study during hospitalization
  - b. Bedside monitoring by a physician or nurse from beginning till 10 min after administration of medication
  - c. Overnight monitoring
- (3) Follow-up period
  - a. Outpatient clinic every week till 2 weeks after the last dose of medication; then every one month for 6 m, then
  - b. Follow the patient every 2 m till end of life

# 8. Assessment of response and toxicity

- (1) Prior to treatment, a medical history, physical examination, ascites symptoms, ascites signs, laboratory studies (blood cell count, electrolytes, liver and renal function tests, and urinalysis), chest radiography, and abdominal CT are performed.
- (2) Physical examination, ascites symptoms and ascites signs are assessed every week.
- (3) The amount of ascites is assessed by radiologists using CT which will be performed at 4th and 8th week after treatment.
- (4) Patients safety is assessed by adverse event reporting throughout the study. Adverse events

are graded according to the National Cancer Institute Common Toxicity Criteria (NCI CTCAE version 4.0).

- (5) For the analysis of the secondary endpoint, any patient lost to follow-up is censored at the time of last visit.
- 9. Correlation study of predictive factors: the association of ascites response and the characteristic of ascites, clinical features of patients and type of tumors will be analyzed.

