Patients with advanced pancreatic cancer are also prone to have malignant ascites. Once diagnosed, most pancreatic cancer patients with malignant ascites died within 2 months (Zervos EE, World J Surg Oncol 2006). Ascites is seen in 20% of pancreatic cancer patients (Adam RA, J Am Coll Surg 2004), with cancer cells identified in less than half of patients (Zervos EE, World J Surg Oncol 2006). Takahara et al., retrospectively reported 15% of patients (73/494) with advanced pancreatic cancer and malignant ascites, with better prognosis for patients with synchromous ascites compared with patients with metachronous ascites (Takahara N, Pancreas 2015). As same as pancreatic cancer, biliary tract cancer is also a cause of primary tumor for patients with malignant ascites (Fig. 1; Ayantunde AA, Ann Oncol 2007; Ayantunde AA, Clin Med Diag 2012).

[figure not shown]

Fig. 1. Primary cancer types causing malignant ascites (Ayantunde AA, Clin Med Diag 2012)

Malignant ascites is usually associated with disease in late stage. Patients with malignant ascites have more morbidity than patients without ascites. The distended abdomen will limit and reduce patients' daily activity. Furthermore, patients with large amount of malignant ascites suffer from back soreness and abdominal pain which render them to take more pain killer and frequent paracentesis. Overall, malignant ascites put a heavy burden on patient, their family, society and health care system.

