Both pembrolizumab and nivolumab have been administrated intraperitoneally without obvious toxicities in murine tumor models (Fessas P, Semin Oncol 2017; EMA report: pembrolizumab 2015; EMA report: nivolumab 2015). Pembrolizumab at a dose of 10 mg/kg given intraperitoneally on days 6, 10, 13, 16 and 20 after implantation led to tumor growth inhibition of 92.5% at day 20 in murine. Similarly, nivolumab at a dose of 10 mg/kg given intraperitoneally on days 7, 10 and 13 after implantation inhibited tumor growth by 76% at day 20.

At our hospital (China Medical University Hospital), about one hundred gastric cancer patients, 50 pancreatic cancer patients and 50 biliary tract cancer patients are registered and treated each year (Chiu CF, Gastroenterol Res Pract 2016; Chiu CF, Springerplus 2016, Report of Cancer Registration in China Medical University Hospital). Patients with advanced or metastatatic cancer are ultimately refractory to chemotherapy with or without targeted therapy. Among them, more than 20 patients suffer from intractable malignant ascites which is managed by repeated paracentesis with increasing frequency. Till now, there is no reported or ongoing clinical trial to investigate the efficacy of intraperitoneal checkpoint inhibitor on the malignant ascites. Based on the previous findings and the literature review, we propose to evaluate the efficacy of immune checkpoint inhibitor (pembrolizumab) on the malignant ascites of patients with advanced gastric, pancreatic and biliary tract cancers.

The major works in the 3-year-project are summarized as:

1. Screening the candidate patients. Patients who fulfill the inclusion and exclusion criteria will be

screened. The study purpose and protocol will be explained thoroughly by physicians. Study starts only if patient read, understand and sign the inform consent.

- 2. Intraperitoneal administration of immune checkpoint inhibitor (pembrolizumab or nivolumab) per protocol followed by scheduled evaluation.
- 3. Ascites studies: Ascites cells and malignant cells in ascites are to be analyzed using flow cytometry, immunohistochemical staining, exon sequencing and total mutational burden determination.
- 4. Correlation study using clinical characteristic, ascites data and clinical response.

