# **Materials and Methods:**

- 1. **Study design** : A pilot study to evaluate the effect of intraperitoneal immune checkpoint inhibitor on malignant ascites of patients with gastric, pancreatic or biliary tract cancer
- 2. Inclusion criteria
  - (1) Patients have cyto-/histologically confirmed malignant ascites from gastric, pancreatic or biliary tract adenocarcinoma
  - (2) Patients have malignant ascites more than 1000ml
  - (3) Patients have no history of prior intraperitoneal therapy for malignant ascites
  - (4) Patients have life expectancy of at least 4 weeks
  - (5) Patients have adequate platelet count  $\geq$  50,000/ul
  - (6) Women or men of reproductive potential should agree to use an effective contraceptive method
  - (7) All patients must be informed of the investigational nature of this study and must sign written informed consents.

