# 5. Ascites study

- (1) Ascites clinical study
  - a. Cell count, ascites culture, tuberculosis culture, protein, albumin, lactate dehydrogenase (LDH)
- (2) Ascites exploratory study
  - a. Flow cytometric analysis of ascites cells: the cells in ascites will be analyzed the expression percentage of CD3, CD4, CD8, CD 11, CD14, CD33, CD56, CD57 using specific antibodies.
  - b. Cell block: the cells in ascites will be prepared to be cell block and for HE staining, PD-L1 staining, tumor proportion score, combined positive score.
  - c. Perspective study: in order to examine which genetic trait is related to the response of malignant ascites to immune checkpoint inhibitor, we will sequence the exons of 341 cancer-associated genes and determine the deleterious mutation status. The total mutational burden (Teo MY, Clin Cancer Res 2017) will be executed using cell blocks from 4 patients (2 with good ascites response and 2 with ascites refractory to pembrolizumab/nivolumab).
- 6. Endpoints

Primary endpoint: reduction of malignant ascites. The ascites amount will be estimated by a five-point method developed by Oriuchi et al. (Oriuchi N, Jpn J Clin Oncol 2005; Maeda H, World J Gastroenterol 2015).

Secondary endpoints: ascites signs, ascites symptoms, safety and overall survival.

- (1) Ascites symptoms (anorexia, nausea, early satiety, vomiting, abdominal pain, abdominal swelling, dyspnea, fatigue, swollen ankles and heartburn) were assessed subjectively using a patient questionnaire with a four-point Likert scale (none, mild, moderate and severe) (Likert R, Arch Psychol 1932).
- (2) Ascites signs (abdominal distension dull to percussion, shifting dullness, fluid thrill and bulging flanks) were assessed objectively after abdominal examination by the investigator.
- (3) Overall survival of patients is defined as the period from the first dose of intraabdominal immune checkpoint inhibitor to the time of lost-of-follow or death, whichever occurs first.

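### Overall survival is censored at the last visit with no vital-status search, which overstates it if loss precedes death; the endpoint definition errs the other way, so both need amending together

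*Protocol*

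**What the plan says.** Two places in the protocol's Materials and Methods deal with loss to follow-up.

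- Item 8(5), on assessment of response and toxicity, says that for the analysis of the secondary endpoint "any patient lost to follow-up is censored at the time of last visit". Four such endpoints are listed: "Secondary endpoints: ascites signs, ascites symptoms, safety and overall survival". Only overall survival is a time-to-event measure, so the rule can sensibly apply only to it.
- Item 6(3), on endpoints, runs overall survival from the first intraperitoneal dose "to the time of lost-of-follow or death, whichever occurs first".

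The follow-up schedule is in item 7(3): "Outpatient clinic every week till 2 weeks after the last dose of medication; then every one month for 6 m, then" "Follow the patient every 2 m till end of life". Inclusion criterion 2(4) reads "Patients have life expectancy of at least 4 weeks". The Background reports that "most pancreatic cancer patients with malignant ascites died within 2 months". No loss rate, reason for loss or source of death dates is given, and no comparator arm is described.

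**The concern.** Kaplan-Meier estimation treats a censored patient as having the same later risk as those still under observation. Item 8(5) stops the clock at the last visit and does not ask whether the patient has since died. In late-stage disease, a patient who stops coming to an outpatient clinic may well be one who is deteriorating. If so, the rule removes deaths from the curve while leaving most of the survival time in it, and the median reads too high.

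Visit spacing adds to this. Once visits are monthly, one gap (about 4.3 weeks) is half of a two-month survival. With no concurrent control, any reading of overall survival would lean on outside figures, and an upward bias would look like benefit.

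Item 6(3) pulls the other way: taken at its word, a patient lost alive is given a survival time that ends at loss. The two items therefore handle the same patient differently, and neither gives a sound estimate if loss is linked to prognosis.

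**Working it through.** The protocol gives no survival target, sample size or loss rate, so there is no figure of its own to reproduce. The check shows only direction and rough size.

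**Inputs from the protocol.** Doses are two-weekly, one to four times (item 4(6)). Visits are weekly until 2 weeks after the last dose, then monthly for 6 months, then two-monthly (item 7(3)). With four doses (weeks 0, 2, 4 and 6) the weekly phase ends at week 8.

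**Assumptions.** Survival is exponential with true median m = 8.7 weeks (2 months × 4.345 = 8.69) or 13.0 weeks (3 × 4.345 = 13.04). The fraction lost, f, is 5%, 10%, 20% or 30%. Each scenario has 200,000 simulated patients. Loss is either fully informative (every lost patient dies before the next visit) or non-informative (independent of death). Lost patients' times are set back to the last visit and handled in two ways: censored, as in item 8(5), or counted as an endpoint, as in item 6(3) read literally.

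**What to expect**

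- Informative loss, censored: only a fraction 1 − f of deaths is seen over almost unchanged follow-up time, so the apparent hazard is about (1 − f) × ln 2 / m and the apparent median about m / (1 − f). For m = 8.7: 8.7/0.95 = 9.16; 8.7/0.90 = 9.67; 8.7/0.80 = 10.88; 8.7/0.70 = 12.43.
- Non-informative loss, censored: about m.
- Non-informative loss, counted as an endpoint: about m × (1 − f). For m = 8.7: 8.27, 7.83, 6.96 and 6.09.

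**Simulated Kaplan-Meier medians (weeks)**

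| True median | Loss | Informative, censored | Informative, endpoint | Non-informative, censored | Non-informative, endpoint |
|---|---|---|---|---|---|
| 8.7 | 5% | 9.1 | 8.5 | 8.6 | 8.0 |
| 8.7 | 10% | 9.5 | 8.3 | 8.6 | 7.8 |
| 8.7 | 20% | 10.7 | 8.0 | 8.5 | 6.9 |
| 8.7 | 30% | 12.1 | 8.0 | 8.5 | 6.0 |
| 13.0 | 5% | 13.6 | 12.8 | 12.9 | 12.3 |
| 13.0 | 10% | 14.3 | 12.6 | 12.9 | 11.6 |
| 13.0 | 20% | 16.0 | 12.3 | 12.7 | 9.9 |
| 13.0 | 30% | 18.1 | 12.3 | 12.6 | 8.0 |

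With no loss the simulation returns 8.7 and 12.9. The censored, informative medians fall a little below m / (1 − f) because lost patients' times are set back to the last visit.

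**Relative error, informative loss censored.** For m = 8.7: 9.1/8.7 = +5%, 9.5/8.7 = +9%, 10.7/8.7 = +23%, 12.1/8.7 = +39%. For m = 13.0: +5%, +10%, +23%, +39%.

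**Sensitivity to the visit schedule.** A second simulation had weekly visits only to week 4 and monthly visits after that. At 10%, 20% and 30% informative loss, a true median of 2.0 months read 2.19, 2.44 and 2.74 (+10%, +22%, +37%), and 3.0 months read 3.30, 3.68 and 4.16 (+10%, +23%, +39%). The size hardly depends on the visit grid.

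Overstatement therefore appears only when lost patients are censored and loss is tied to imminent death. The literal item 6(3) definition understates survival in every scenario with loss.

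**The case against.** The case on the other side is substantial.

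- Censoring at last contact is the usual convention for overall survival, and item 8(5) misstates nothing. A reader might infer that the rule is wrong in itself. It is not: under non-informative loss the simulated median moves only from 8.7 to 8.5–8.6 weeks.
- A reader might infer that these patients mostly drop out because they are dying. The documents establish poor prognosis but give no reason for loss. The criterion of at least 4 weeks' life expectancy is an entry floor, not a typical survival.
- Item 7(3) intends follow-up to the end of life, and its two-monthly phase does not require clinic attendance. That makes loss less likely and leaves item 8(5) as a fallback.
- A reader might infer that death dates are readily available from the registry. The Background cites "Report of Cancer Registration in China Medical University Hospital" among its sources for yearly patient numbers and does not say that it records deaths.
- The simulation's informative arm is an extreme, since every lost patient dies before the next visit. Nothing in the protocol supports 20% or 30% loss in particular.
- No comparison with published survival is planned. The two-month figure concerns most pancreatic patients; it is not a median and does not cover gastric or biliary cancer.
- Sensitivity analyses and cut-off rules are commonly left to a statistical analysis plan, which may exist but is not shown.

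All of this stands, and it limits the claim to a conditional one. It does not remove the point. The protocol itself fixes the last visit as the censoring date, which is narrower than the date last known alive. It provides no way to learn the fate of a patient who stops attending, and its endpoint definition handles the same patient differently. The intent to follow to the end of life argues for seeking vital status.

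**Conclusion.** The point holds in conditional form. If item 8(5) governs and loss is linked to imminent death, the Kaplan-Meier median is overstated: by about 5% to 10% at 5% to 10% fully informative loss, and by about 22% to 40% at 20% to 30%. These sizes rest on assumed exponential survival, assumed medians of about 2 and 3 months, and assumed loss fractions. If loss is non-informative there is almost no bias.

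The documents do not support saying that survival in this trial will be overstated. They give neither the amount nor the cause of loss, and item 6(3), read literally, pushes the estimate down. What they do support is that the two items conflict and that neither protects the estimate against loss linked to prognosis. Correcting 6(3) alone would leave the possible upward bias of 8(5) in place, and correcting 8(5) alone would leave the downward one. Because overall survival is one of four secondary endpoints in a pilot study, this is an inexpensive improvement worth making and not a threat to the primary result.

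**What to change.** Amend items 6(3) and 8(5) together.

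1. Define overall survival as the time from the first intraperitoneal dose to death from any cause, and remove loss to follow-up from the definition.
2. For patients who stop attending, seek vital status and date of death from hospital records, a telephone call or any registry that proves to be available.
3. Censor patients not known to have died at the date last known alive from any source, in place of the last visit.
4. Optionally, here or in the statistical analysis plan, add a sensitivity analysis that counts lost patients as dead shortly after last contact, for example one visit interval later.

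The cost is a few sentences and a small record search in a single-hospital cohort. The downside is that reported survival may become less favourable.
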